Figure 4. Protocol of the experimental visits. Visits will be identical except for the oral drug or supplement administration before any procedure.

STATISTICAL ANALYSES: Sample size estimation (statulator.com) is 11 individuals per group, based on the femoral artery blood flow response to knee extension exercise from our preliminary data (see below), using Student's *t*-test for independent samples, and considering a two-tailed alpha of 0.05, and power of 0.8 as parameters. This estimated sample size is adequate relative to our previous investigations^{10,11}. Due to potential influence of sex and race on vascular function⁶⁹, we will duplicate the estimated sample size to recruit an equal number of men and women. To account for incompleteness and exclusion of data during analyses, additional participants will be recruited, leading to an estimate of 30 individuals enrolled in each racial group. We will use a mixed-model ANOVA to compare vascular responses according to the effects of drug administration (Placebo vs. Drug), group (Black vs. White), and interaction. Subjects' characteristics will be compared using Student's *t*-test for independent samples and, in case of significant differences, such characteristics will be used as covariates in the ANOVA. Additionally, while men and women will be primarily grouped according to race, the large and balanced sample size will allow for sub-analyses comparing the effects of race on vascular responses separately in men and women.

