- Reduction in the ET-1 constrictor signal with Bosentan will increase vascular responses in Black individuals, attenuating the impairment in comparison with White individuals.

Some alternative approaches to be attempted in future studies include:

- Direct intra-arterial infusions of vasoactive compounds (e.g., L-arginine, L-NMMA, selective blockers of ET_A and ET_B receptors, etc.) to evoke quick local responses with lower concentrations, preventing systemic cardiovascular effects⁷⁰, and allowing for deeper mechanistic insight.
- Chronic oral administration of beetroot juice, L-citrulline, Sildenafil, and Bosentan with multiple follow-up assessments, to evaluate the persistence of improvements on vascular responses, whether maladaptive mechanisms become expressed and prevent vascular improvements, effects on blood pressure control, etc.
- Harvesting of endothelial cells via catheterization to establish correlations between vascular responses and cellular ET-1 levels (higher specificity than plasma measurement), expression of ET_B receptors (known to evoke NO production in the endothelium), eNOS, etc.
- Use of the stored blood samples collected in this study to examine molecular markers of other vasoactive mechanisms (e.g., reactive oxygen species, ADMA, ATP, angiotensin II, catecholamines, etc.) to establish correlations with the vascular responses, as well as for the design of novel hypotheses and future studies.
- The large and balanced sample size of men and women will allow for secondary analyses that may corroborate, as previously suggested⁶⁹, a differential effect of race on vascular function between men and women.

External funding opportunities will be pursued (see below) to support the completion of the current specific aims, as well as new studies in the field as new questions arise:

- NIH Research Project Grant (R01): Parent Funding Opportunity Announcement (PA-19-091), submitted to National Institute on Minority Health and Health Disparities (NIMHD).
- NIH Notice of Special Interest (NOT-HL-19-711): To support epidemiological research to assess cardiovascular health during childhood and its relationship to adult disease in underrepresented populations. Submitted through the R01 mechanism (PA-19-056) to National Heart, Lung, and Blood Institute (NHLBI).

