Healthy Black and White men and women will be recruited between the ages of 18 to 40 years. The focus of our research is to examine differences in vascular function associated with race. Therefore, to avoid individuals with impaired vascular function due to aging and comorbidities, we will recruit a relatively young cohort of participants.

INCLUSION OF WOMEN AND MINORITIES

This research proposal is designed to elucidate deleterious alterations in vascular function specifically in young Black individuals. Accordingly, Black men and women will be examined and, as traditionally done in previous studies in this field, results will be compared with those from White men and women. Subjects will qualify for the study if they identify their race and the race of their biological parents as being Non-Hispanic Black (i.e., African American) or Non-Hispanic White (i.e., Caucasian American). Individuals whose parents are mixed Black and White, or of other races (Hispanic or Latino, Asian, Native American, etc.) will not qualify for the study. To avoid confounding factors associated with lifestyle, only individuals born and raised in the U.S. will be included. We anticipate to include a total of 60 individuals, with a distribution of 15 Black men, 15 Black women, 15 White men, and 15 White women. While men and women will be primarily grouped according to race, this large and balanced planned sample size will allow for sub-analyses comparing the effects of race on vascular responses separately in men and women.

RECRUITMENT AND RETENTION PLAN

Individuals will be recruited via UMMC e-mail listserv, UMMC intranet, flyers on campus, and word of mouth. Potential participants will contact the study personnel via e-mail or phone, and answer screening questions. If they meet the inclusion criteria, a consenting and familiarization visit will be scheduled. Consenting will be conducted at the research laboratory by a study person. After signing the Informed Consent Form, participants will answer a medical history questionnaire, and be familiarized with the research measurements and procedures.

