Sample size estimation (statulator.com) is 11 individuals per group, based on the femoral artery blood flow response to knee extension exercise from our preliminary data, using Student's t-test for independent samples, and considering a two-tailed alpha of 0.05, and power of 0.8 as parameters. This estimated sample size is adequate relative to our previous investigations. Due to potential influence of sex and race on vascular function, we will duplicate the estimated sample size to recruit an equal number of men and women. To account for incompleteness and exclusion of data during analyses, additional participants will be recruited, leading to an estimate of 30 individuals enrolled in each racial group. We will use a mixed-model ANOVA to compare vascular responses according to the effects of drug administration (Placebo vs. Drug), group (Black vs. White), and interaction. Subjects' characteristics will be compared using Student's t-test for independent samples and, in case of significant differences, such characteristics will be used as covariates in the ANOVA. Additionally, while men and women will be primarily grouped according to race, the large and balanced sample size will allow for sub-analyses comparing the effects of race on vascular responses separately in men and women.

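### A sex difference in the race effect needs a race-by-sex interaction; separate race tests in men and women cannot establish it, and the cells are sized for those tests only

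*Combined protocol and SAP*

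**What the plan says.** The Statistical Analyses paragraph of the Research Strategy, and the same text under Statistical Design and Power, give the starting number: "Sample size estimation (statulator.com) is 11 individuals per group". It comes from one pilot outcome, leg blood flow during knee extension, and from a two-sample t-test at a two-sided 5% level with 80% power. That number is doubled so that men and women are equally represented, then raised to 30 enrolled per race to cover lost data. Inclusion of Women and Minorities gives the total of 60 "with a distribution of 15 Black men, 15 Black women, 15 White men, and 15 White women".

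The planned mixed-model ANOVA contains drug, race group and their interaction. Sex does not appear. Men and women are grouped mainly by race, and sex is handled by a further statement: "the large and balanced sample size will allow for sub-analyses comparing the effects of race on vascular responses separately in men and women". Inclusion of Women and Minorities makes the same promise.

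The last bullet before the funding list in Expected Results and Future Plans again relies on the large, balanced sample of men and women. It says that secondary analyses may corroborate "a differential effect of race on vascular function between men and women". No method is given there. No race-by-sex term is named anywhere in the documents, and no power is given for one.

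**The concern.** A statement that race acts differently in men and women is a statement about the difference between two race effects. The only sex analysis described gives two separate race comparisons, one per sex. Neither estimates that difference or attaches an error rate to it. One comparison can be significant and the other not when the two race effects are identical, because each is a noisy test on small groups.

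The sample is also presented as large enough for the sex question, although the sizing calculation concerns a two-group race comparison and rests on men only (Preliminary Study: 4 White, 8 Black). At stake is a published claim that racial vascular dysfunction is specific to one sex, or a failure to see a real difference, with readers told that the sample was adequate.

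**Working it through.** **Inputs from the documents.** 11 per group; two-sided alpha 0.05; power 0.80; independent-samples t-test; doubling for sex; 30 enrolled per race; 15 enrolled per race-by-sex cell; preliminary group P = 0.038 from 4 and 8 men.

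**Inputs that are assumptions.** No mean difference or SD is printed (the preliminary results are in a figure that is not shown), so the planning effect d is back-solved. A second value, d = 0.8, illustrates a smaller effect and is not in the documents. SDs are taken as equal across cells, and the calculation covers one outcome at one visit.

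**Step 1: the plan's 11.** It cannot be reproduced directly. As a rough check, if P = 0.038 is treated as a t-test on 10 df, t = 2.389 and d = 2.389 × √(1/4 + 1/8) = 1.46, or 1.35 after small-sample correction. Exact-t sizing then gives 9 or 10 per group. So 11 is plausible but unverified. Working backwards, 11 per group at 80% power corresponds to d between 1.26 and 1.32. I use 1.26.

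**Step 2: cell sizes.** 11 × 2 = 22 per race, so 11 per cell. 30 / 2 = 15 per cell enrolled. The step from 22 to 30 allows for a loss of 1 − 22/30 = 27%.

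**Step 3: race test within one sex.** Noncentrality = d × √(m/2), df = 2m − 2, with m the cell size. For d = 1.26 (unrounded 1.256) this is 2.95 at m = 11 and 3.44 at m = 15.

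**Step 4: chance of a split result when the race effect is the same in both sexes.** Men and women are different people, so with within-sex power p the chance that exactly one test is significant is 2p(1 − p). At d = 1.26: 2 × 0.80 × 0.20 = 0.32 (m = 11) and 2 × 0.913 × 0.087 = 0.16 (m = 15). At d = 0.8: 2 × 0.431 × 0.569 = 0.49 and 2 × 0.562 × 0.438 = 0.49.

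**Step 5: race-by-sex interaction.** The contrast is the race difference in women minus the race difference in men. SE = SD × √(4/m), df = 4(m − 1). For m = 11, SE = 0.603 SD with 40 df; for m = 15, SE = 0.516 SD with 56 df. If the full 1.26 SD effect is in one sex and absent in the other, noncentrality is 1.256/0.603 = 2.08 or 1.256/0.516 = 2.43.

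| Quantity | 11 per cell | 15 per cell |
|---|---|---|
| Within-sex race test, power at d = 1.26 | 80% | 91% |
| Within-sex race test, power at d = 0.8 | 43% | 56% |
| Exactly one sex significant, same d = 1.26 in both | 32% | 16% |
| Exactly one sex significant, same d = 0.8 in both | 49% | 49% |
| Interaction power, difference of 1.26 SD | 53% | 67% |
| Interaction power, difference of 0.63 SD (half) | 17% | 22% |
| Difference detectable with 80% power | 1.73 SD | 1.47 SD |

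For 80% interaction power at a difference of 1.26 SD, 21 per cell (84 in total) would be needed. The last row of the table does not depend on d. Both of its values exceed the whole implied planning effect, even at the upper end of 1.32.

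**The case against.** The strongest reply is that the plan keeps its promise. The statistical sections promise race comparisons within each sex, and doubling the sample sizes exactly those comparisons. A reader might infer that the cells are too small for the within-sex tests. The documents do not support that: at the effect implied by the plan's own 11, each test has 80% power, rising to 91% if all 15 per cell are evaluable. This stands, with the reservation that the effect comes from 12 men and may be optimistic.

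Second, a reader might infer that the plan intends to declare a sex difference because one sex is significant and the other is not. It does not say so. The differential-effect wording sits in a list introduced as approaches for future studies and names no method. This also stands as a limit. But that bullet refers to this study's sample, and the separate sub-analyses are the only sex analysis described.

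Third, the split-result rate depends on assumptions. It is 16% rather than 32% at 15 per cell, and the 49% rests on an effect size that is not in the documents. That is correct, so the range should be read as a whole.

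Finally, sex is secondary, and the Bosentan protocol plans no sex sub-analysis; it uses sex only to balance randomization. Its ANOVAs also lack a sex term, but that is not a fault on this point.

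**Conclusion.** The concern holds for the claim about a sex difference, and only for that claim. Separate race tests in men and women cannot corroborate a differential race effect, and the plan names no analysis that can. With 11 to 15 per cell, the race-by-sex contrast has 80% power only for differences of 1.73 to 1.47 SD. Its power is 53% to 67% even if the whole implied race effect is confined to one sex. With identical effects, a split result occurs in 32% (11 per cell) or 16% (15 per cell) of trials at d = 1.26, and in about 49% at an assumed d = 0.8.

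The detectable differences rest on equal SDs and a single outcome at one visit; the other figures also rest on the assumed d. None of them carries over to a race-by-sex-by-drug term, whose power depends on a within-person correlation that the documents do not give. A reader might take this as undermining the main results. It does not: the primary race, drug and race-by-drug tests are not affected. The change should be made, but it concerns a secondary analysis.

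**What to change.** 1. Add sex and race-by-sex to the mixed model and, where drug effects are examined by sex, race-by-sex-by-drug.
2. Base any claim that the race effect differs between men and women only on the interaction estimate and its confidence interval.
3. Report race effects in men and in women, with confidence intervals, from that same model.
4. Label the sex-difference analysis secondary and exploratory.
5. In Expected Results and Future Plans, qualify the reliance on a large and balanced sample: under the stated assumptions the race-by-sex contrast can detect, with 80% power, only differences of about 1.5 to 1.7 SD. Claim no figure for race-by-sex-by-drug.

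The cost is a few extra model terms, revised wording and a less favourable stated capability. No participants, visits or procedures are added.

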Enclosure(s): (1) Investigator Responsibilities, Protection of Human Research Participants

UMMC Investigator Responsibilities

Protection of Human Research Participants

The IRB reviews research to ensure that the federal regulations for protecting human research participants outlined in UMMC policy, the Department of Health and Human Services (DHHS) regulations (45 CFR 46) and the Food and Drug Administration (FDA) regulations (21 CFR Parts 50 & 56), as well as other requirements, are met. The University of Mississippi Medical Center's Federalwide Assurance (FWA), FWA# 00003630, awarded by the Office for Human Research Protections (OHRP) at DHHS, is a written pledge to follow federal guidelines for protecting human research participants in accordance with the principles of the Belmont Report. **All investigators must read both the Belmont Report and the UMMC FWA to understand their responsibilities in conducting research involving human participants.** Both documents are available on the Human Research Office webpage, <http://irb.umc.edu/>, and in hard copy by request from the Human Research Office. Some of the responsibilities investigators have when conducting research involving human participants are listed below.

1. Conducting the Research: You are responsible for making sure that the research is conducted according to the IRB approved research protocol. **You are also responsible for the actions of the study's co-investigators and research staff.**
2. Participant Enrollment: You may not recruit or enroll participants prior to the IRB approval date or after the expiration date of IRB approval. All recruitment materials for any form of distribution or media use must be approved by the IRB prior to their use. If you need to recruit more participants than was noted in your IRB approval letter, you must submit an amendment requesting an increase in the number of participants.
3. Informed Consent: Informed consent is a process that begins with the initial contact and ends at some point after the study is complete. You are responsible for the conduct of the consent process, ensuring that effective informed consent is obtained and documented using **only** the IRB-approved and stamped consent document(s), and for ensuring that no human participants are involved in research prior to obtaining their informed consent. Whoever is presenting the consent document to the potential participant and conducting the consent discussion must have all pertinent information at hand, be knowledgeable about the study and the disease or condition involved, if any, and have the ability and experience to answer questions regarding the study and any treatment involved. Please give all participants a signed copy of each consent or assent document they sign, and keep the originals in your secured research files for at least six (6) years. When appropriate, you should place a copy of the consent document in the participant's medical record.

4. Continuing Review: The IRB must review and approve all IRB-approved research protocols at intervals appropriate to the degree of risk, but not less than once per year. **There is no grace period.** Prior to the date on which IRB approval of the research expires, the IRB will send you three reminders to submit a Continuing Review, 90, 60 and 30 days prior to expiration. Although reminders are sent, **it is ultimately your responsibility to submit the renewal in a timely fashion to ensure that a lapse in IRB approval does not occur.** If IRB approval of your research lapses, you must stop new participant enrollment, and contact the IRB immediately.
5. Amendments and Revisions: If you wish to amend or change any aspect of your research, including research design, interventions or procedures, number of participants, participant population, consent document, instruments, surveys or recruitment and retention material, you must submit the amendment or revisions to the IRB for review with a Request for Change. You **may not initiate** any amendments or changes to your research without first obtaining IRB review and written approval. The **only exception** is when the change is necessary to eliminate apparent immediate hazard to participants. In that case the IRB should be immediately informed of this necessity, but the change may be implemented before obtaining IRB approval.
6. Unanticipated Events: All adverse events that are unanticipated (**unanticipated means that the event is unexpected, possibly related and places participants at greater risk of harm than previously recognized**) and serious protocol deviations, must be reported to the IRB **within fourteen (14) days** of discovery of the incident. Any research related injury occurring at a UMMC performance site or to a UMMC study participant and participant complaints must also be reported, along with any instances of serious or continuing problems, or non-compliance with the IRB's requirements for protecting human research participants. The only exception to this policy is death - **the death of a UMMC research participant must be reported within 48 hours.** All reportable events should be submitted to the IRB with the Adverse Event/Unanticipated Problem Report form.

Events that do not meet the definition of an unanticipated problem involving risk to participants or others, including research related injury occurring at a UMMC performance site or to a UMMC study participant, participant complaints, problems, minor protocol deviations and non-compliance with the IRB's requirements for protecting human research participants should be reported as follows: Minor deviations and problems should be submitted at the time of continuing review, as instructed on the form. All other events should be reported in writing via letter or email to the IRB with sufficient detail to allow the reviewer to understand the problem and any actions taken to prevent it from happening again.

7. Research Record Keeping: At a minimum, you must keep the following research related records in a secure location for at least six years: the IRB approved research protocol and all amendments; all versions of the investigator's brochure; all informed

consent documents; all recruiting materials; all renewal applications; all adverse or unanticipated event reports; all correspondence to and from the IRB; and all raw data.

8. Reports to FDA and Sponsor: When you submit the required annual report to the FDA or you submit required reports to your sponsor, you **must** provide a copy of that report to the IRB. You may submit the report with your IRB continuing review application.
9. Provision of Emergency Medical Care: When a physician provides emergency medical care to a participant without prior IRB review and approval, to the extent permitted by law, such activities will not be recognized as research and the data cannot be used in support of the research.
10. Final Reports: When you have completed the study, (no further participant enrollment, interactions, interventions or data analysis) or stopped work on it, you must submit a Final Report to the IRB using the Final Report form.
11. On-Site Evaluations, FDA Inspections, or Audits: If you are notified that your research will be reviewed or audited by the FDA, OHRP, the sponsor, any other external agency, or any internal group, you **must** inform the IRB immediately and submit all audit reports received as a result of the audit to the IRB.

If you have questions or need assistance, please contact the Human Research Office at [contact].

RESEARCH PROTOCOL

Title	Racial Differences in Cardiovascular Function: The Role of Endothelin-1
Principal Investigator	[name].
Co-Investigators	[name] [name]. [name]. [name]. [name].
Abstract	The current study will examine the role of Endothelin-1 (a potent endogenous vasoconstrictor; ET-1) on brachial and popliteal artery flow-mediated dilation, reactive hyperemia, and blood flow responses to passive leg movement, rhythmic handgrip exercise, and rhythmic knee extension exercise in Black and White individuals. In two separate visits, we will administer an acute oral dose of Bosentan (antagonist of ET-1 receptors ET _A and ET _B) or Placebo (randomized double-blind cross-over design), followed by examination of brachial artery flow-mediated dilation and reactive hyperemia at rest, as well as blood flow responses to passive leg movement, low, moderate, and high-intensity rhythmic handgrip exercise and rhythmic knee extension exercise in Black and White individuals.
Background	Black (i.e. African American) individuals develop cardiovascular diseases earlier in life and at greater rates than other racial groups ¹⁻³ . Because of this greater risk, studies assessing racial differences in cardiovascular physiology are needed. It has been demonstrated that, compared with White individuals (i.e. Caucasian American, the largest racial group in the U.S. population), healthy young Black individuals have impaired vascular responses to various stressors, characterized by augmented vasoconstriction and reduced vasodilation ⁴⁻⁸ . However, much remains unknown regarding the mechanisms by which these individuals demonstrate vascular dysfunction. Techniques to assess acute vascular function consist of applying stimuli to evoke dilation in the macro- and microvasculature. For example, the prolonged inflation and subsequent deflation of a pneumatic cuff on the forearm or calf evoke brachial or popliteal artery flow-mediated dilation and forearm reactive hyperemia, which have been associated with cardiovascular health ⁹ . Furthermore, the vasodilator responses to passive leg movement, rhythmic handgrip exercise, and rhythmic knee extension exercise are also considered sensitive for the detection of vascular dysfunction ¹⁰⁻¹² . Multiple mechanisms interact and determine the magnitude of these dilator responses, with vasoconstrictor factors (ET-1, adrenergic receptors, angiotensin II, etc.) causing attenuation, and vasodilator factors (NO, intravascular ATP, adenosine, K ⁺ channels, EDHF, etc.) causing an increase in vascular responses ¹³ .

Purpose	
To begin to elucidate the alterations in vascular function in Black individuals, we chose to target ET-1, a peptide produced by the vascular endothelium that mediates vasoconstriction by binding ET_A and ET_B receptors on smooth muscle^{14,15}. ET-1 seems to play a prominent role in the pathophysiology of hypertension specifically in Black patients^{16,17}. Also, it is suggested that ET-1 may be associated with impaired vascular control of blood pressure in young normotensive Black men¹⁸. Vascular responsiveness to ET-1 is also upregulated in adults exposed to insults during their fetal life (e.g., poor maternal nutrition, chronic stress, no prenatal care), psychological stressors during childhood (e.g., physical and emotional abuse, household dysfunction), and high ethnic discrimination¹⁹⁻²⁴—all of which are more prevalent among Black than White individuals, possibly contributing to racial disparities in vascular function²⁵⁻²⁸. We hypothesize that Black individuals have reduced vasodilator responses as a consequence of a greater vasoconstrictor tone mediated by ET-1. Therefore, we hypothesize that the antagonism of ET_A and ET_B receptors will reduce the vasoconstrictor tone and augment the vasodilator responses in Black but not in White individuals.

Specific Aim	
We will examine the role of ET-1 on brachial and popliteal artery flow-mediated dilation, reactive hyperemia, and blood flow responses to passive leg movement, rhythmic handgrip exercise, and rhythmic knee extension exercise between Black and White individuals. Using an acute oral administration of Bosentan, we will antagonize ET_A and ET_B receptors to reduce the vasoconstrictor tone mediated by ET-1 and, consequently, allow for greater flow-mediated dilation, reactive hyperemia, and blood flow responses to passive leg movement, handgrip, and knee extension. We anticipate that this effect of Bosentan will be more prominent in Black individuals than in White individuals. In a separate visit, the participants will receive a Placebo to serve as a control. We will also examine prenatal and at-birth medical records, and apply questionnaires of adverse childhood experiences and perceived discrimination to assess whether these early-life risk factors are associated with racial disparities in vasodilation between Black and White individuals.

Study Period	
3 years Anticipated start date: 09/01/2020 Anticipated end date: 09/01/2023

Data Generation Period	N/A


Study Design
	
The study will consist of three visits to the research clinic (Clinical Research and Trials Unit at the UMMC campus) over 4 months. If a participant misses an appointment, rescheduling will be attempted twice. Women will provide a urine sample for a pregnancy test and answer questions about the most recent menstrual period before any research measurement or procedure be performed in any visit.
 
Visit 1: Informed Consent Form, written consent for access to their prenatal and at-birth medical records, assessment of medical history, application of the questionnaires “Adverse Childhood Experiences (ACE)” and “Scale of Ethnic Experiences (SEE)”, collection of blood samples and endothelial cells from the antecubital vein, familiarization with measurements and procedures that will take place in the next visits, and a rhythmic knee extension maximal exercise test. Visit 1 will last for about 2 hours.
 
Visit 2: Qualifying participants will participate in Visit 2 within 4 weeks after Visit 1. At the beginning of the visit, we will randomly administer either a single oral dose of Bosentan (125 mg) or Placebo. Two hours after administration, we will perform the research measurements and procedures as explained below. This visit will last for about 4 hours.
 
Visit 3: Those who complete Visit 2 will participate in Visit 3, which will take place 1 to 12 weeks later. All research measurements and procedures will be identical, except for the drug administration. At the beginning of the visit, we will administer either Bosentan (125 mg) or Placebo, whichever was not administered in Visit 2.
 
Summary of the Research Measurements:
 
 • Anthropometrics: Height, weight, waist, and hip for characterization. • Electrocardiogram: Adhesive patches placed on the chest and abdomen for heart rate. • Respiration: An elastic belt placed around the abdomen for respiratory movements. • Blood pressure: Brachial blood pressure will be measured throughout the study with an automated blood pressure monitor for validation of the finger blood pressure values. • Finger blood pressure: A small cuff placed around one of the fingers for continuous recording of beat-to-beat blood pressure. • Arm blood flow: Duplex Doppler ultrasound will be used for measurements of brachial artery diameter and blood velocity, used for calculation of blood flow. • Leg blood flow: Duplex Doppler ultrasound will be used for measurements of popliteal and femoral artery diameter and blood velocity, used for calculation of blood flow.
----------------------------	---

- ET-1 expression: Plasma and endothelial lysates will be collected from the antecubital vein using a catheter and J-wires. ET-1 peptide will be measured using an ELISA kit. RNA from endothelial cells will be isolated and reverse transcribed. The resulting cDNA will be used to quantify ET-1 mRNA copy count by Droplet Digital polymerase chain reaction using TaqMan primer gene expression assays with human preproET-1 primers.
- Insults during fetal life: Prenatal and at-birth medical records of each participant will be obtained from the UMMC and local hospitals database in paper copies and digital formats (*e.g.*, EPIC, DataArk). We will assess maternal comorbidities, such as over- or undernutrition, pre-eclampsia, diabetes, obesity, smoking, and alcohol consumption. Gestational age at birth will be assessed and classified as preterm (less than 37 weeks), early-term (37 weeks to 38 weeks 6 days), full-term (39 weeks to 40 weeks 6 days), late-term (41 weeks to 41 weeks 6 days), or post-term (over 42 weeks)²⁹. Also, the birth weight will be assessed, and birth weight of fewer than 2500 grams will be a marker of impaired fetal growth²⁶.
- Adverse childhood experiences: The questionnaire ACE will measure the prevalence of 10 types of trauma over the first 18 years of life: emotional abuse, physical abuse, sexual abuse, emotional neglect, physical neglect, household substance abuse, domestic violence against mother (stepmother), household incarceration, household mental illness, and parental divorce²⁷.
- Perceived discrimination: The questionnaire SEE will measure the magnitude of perceived discrimination, ethnic identity, mainstream comfort, and social affiliation²⁸.

Summary of Research Procedures

- Bosentan or Placebo: A single oral dose of Bosentan (125 mg; Tracleer, Actelion Pharmaceuticals US, San Francisco, CA) or Placebo will be administered in separate visits in a randomized, double-blind, crossover design. Bosentan is an FDA-approved medicine used for the treatment of cardiovascular diseases such as pulmonary hypertension. Pharmacists of the Investigational Drug Services at UMMC will prepare Bosentan and Placebo in liquid suspensions.
- Arm blood vessel response: Participants will lie down on a bed with the arm abducted and elbow extended on a bedside table. A cuff will be placed around the forearm. After baseline arm blood flow measurements, the cuff will be rapidly inflated (< 1 s) and remain inflated for 5 min. Measurements will resume at the last 30 s of cuff inflation and continue for 3 min after rapid cuff deflation.
- Leg blood vessel response: Participants will lie down on a bed with the legs extended and slightly rotated medially. A cuff will be placed around

	
the calf. After baseline popliteal blood flow measurements, the cuff will be rapidly inflated (< 1 s) and remain inflated for 5 min. Measurements will resume at the last 30 s of cuff inflation and continue for 3 min after rapid cuff deflation.
 
 • Passive leg movement: Participants will lie down with their upper body and thighs on a bed, and the lower legs off the bed. One lower leg will be extended on a bedside table, and the other lower leg will hang downwards with the knee flexed at a 90° angle. After baseline femoral blood flow measurements, a researcher will move the participant's right lower leg (knee extension) through the range of motion of 90°–180°–90° for a maximum of 2 min, with continuous measurements of electrocardiogram, respiration, finger blood pressure, and leg blood flow. • Handgrip exercise: Participants will lie down on a bed with the arm abducted and elbow extended on a bedside table. Participants will perform rhythmic handgrip exercise by squeezing a handgrip dynamometer. Each handgrip exercise trial will last a maximum of 6 min or until fatigue. Participants will perform three to six handgrip exercise trials with continuous measurements of electrocardiogram, respiration, finger blood pressure, and arm blood flow. • Knee extension exercise: Participants will sit on a custom ergometer with the arms supported by side tables and one foot on a boot connected to the ergometer. Participants will perform rhythmic knee extension exercise by extending their lower leg through the range of motion of 90°–180°–90°. Each knee extension exercise trial will last a maximum of 6 min or until fatigue. Participants will perform three to six knee extension exercise trials with continuous measurements of electrocardiogram, respiration, finger blood pressure, and femoral blood flow. • Ischemic preconditioning: Participants will lie down on a bed with the arms and legs extended. A cuff will be placed around the upper arms or thighs. The cuffs will be rapidly inflated (< 1 s) and remain inflated for 5 min, then deflated for 5 min. This cycle will be repeated up to 4 times. • Ischemia–reperfusion: Participants will lie down on a bed with the arms and legs extended. A cuff will be placed around the upper arms or thighs. The cuffs will be rapidly inflated (< 1 s) and remain inflated for a maximum of 20 min continuously.
Inclusion Criteria	
 • Black (i.e. African American) or White (i.e. Caucasian American) individuals • 18 to 35 years of age • Born and raised in the United States • Biological parents of the same race (i.e. either Black or White)

Exclusion Criteria	
 • Known chronic or ongoing disease, or on prescribed pharmacological treatment • History of liver disease • Pregnant, trying to become pregnant, or breastfeeding women • Use of hormonal contraceptives • Smoking or vaping in the last 6 months • Body mass index > 35 kg/m²
Number of Participants (anticipated)	
50 participants (i.e. 25 on each racial group). Based on data from Schreuder et al.³⁰, taking the improvement of blood flow response to rhythmic handgrip with Bosentan as the primary outcome, the estimated sample size is 42 participants (i.e. 21 per group). We anticipate having to recruit about 20% more individuals to account for possible loss of data (e.g. participants who cannot complete all visits, problems during analyses, etc.), therefore needing to enroll 50 participants.

Screening and Consent Process	
Announcements will be made via UMMC e-mail listserv, UMMC intranet, Research Participant Recruitment app, flyers on campus, and word of mouth. Potential participants will contact the study personnel via e-mail or phone, and answer screening questions. If they meet the inclusion criteria, Visit 1 will be scheduled. Consenting will be conducted in Visit 1 at the research clinic by [name] or by a study person after supervision and adequate training with [name]. Following consenting, there will be assessments of medical history, and familiarization with the research measurements and procedures. After that, those who qualify for the study will be scheduled for Visit 2 and, subsequently, Visit 3.

